## **2.2 PRETREATMENT EVALUATION**

- 2.2.1** Baseline testing and evaluations that do not impact eligibility
  - 2.2.1.1** Baseline MDASI-SP or MDASI-BT questionnaire (Appendix **12.7** or **12.8**).
  - 2.2.1.2** Total protein, albumin, calcium, phosphorus, glucose, BUN, uric acid, alkaline phosphatase, LDH, and when appropriate, anticonvulsant levels will be performed prior to initiation of treatment.
  - 2.2.1.3** PT, PTT and INR (obtained only on patients receiving warfarin therapy).
- 2.2.2** Baseline testing and evaluations that do impact eligibility.
  - 2.2.2.1** H&P to include prior therapy for the current cancer, blood pressure, Concurrent Medications, KPS and Neurologic examination within 14 days prior to registration.
  - 2.2.2.2** Brain or spine MRI within 14 days prior to registration. Patient must be on a steroid dose that has been stable or decreasing for at least 5 days. If the steroid dose is increased between the date of imaging and registration, a new baseline MRI is required.
  - 2.2.2.3** **NOTE:** Residual disease following resection of recurrent tumor is not mandated for eligibility into the study. To best assess the extent of residual disease post-operatively, an MRI should be done no later than 96 hours in the immediate postoperative period or at least 4 weeks postoperatively, within 14 days prior to registration. If the "within 96-hour of surgery" scan is more than 14 days before registration, the scan needs to be repeated
  - 2.2.2.4** Baseline Cardiac Testing to be performed within 14 days prior to registration includes:
    - EKG.
    - Echo or MUGA scan (MUGA preference as clinically indicated). These studies must be performed under the supervision of an experienced cardiologist, presumably at the same high-volume laboratory for the duration of the trial. The method used for LVEF assessment in an individual subject must be the same

throughout the trial. The guidelines of the American Society of Echocardiography will be used. These guidelines can be located on the www at <http://www.asecho.org/Guidelines.php>.

**2.2.2.5** Baseline Laboratory examinations to be conducted within 14 days prior to registration include:

- CBC with Differential and Platelets.
- Chemistries to include: SGPT (ALT), bilirubin, serum creatinine.
- Serum Pregnancy Test: Beta-HCG in women with childbearing potential.

**2.3 REGISTRATION PROCEDURES**

**This protocol is no longer open to accrual or registration.**

**3 STUDY IMPLEMENTATION**

**3.1 STUDY DESIGN**

This is a phase II study to determine the efficacy of the combination of temozolomide and lapatinib in recurrent brain ependymoma and anaplastic ependymoma as measured by median progression-free survival. Eligible patients will receive 2 cycles of the combination of temozolomide and lapatinib. The temozolomide will be administered at a dose of 125 mg/m^2 as a single daily dose on days 1-7 and 15-21 of a 28-day cycle. The lapatinib will be given as a single daily dose of 1250 mg orally. Patients who do not experience any grade 1 or greater myelotoxicity will be eligible to have the temozolomide dose increased to 150 mg/m^2 as a single daily dose on days 1-7 and 15-21 of a 28-day cycle. The lapatinib dose will not be increased.

Patients who exhibit response to protocol therapy and have not experienced any significant or intolerable toxicities may continue to receive protocol therapy up to a maximum number of 24 cycles. Patients that are showing sustained Complete Response (CR), Partial Response (PR) or Stable Disease (SD) may continue Post protocol single agent therapy with lapatinib. Post-protocol lapatinib supply may be obtained through Glaxo Smith-Kline (GSK). Patients on post protocol single agent lapatinib will have follow up visits every 2 months for survival assessment and radiographic evaluation of disease per MRI or CT scan.

### **3.2 DRUG ADMINISTRATION**

3.2.1 The first and second cycle will consist of the combination of temozolomide and lapatinib. The temozolomide will be administered at a dose of 125 mg/m^2 as a single daily dose on days 1-7 and 15-21 of a 28-day cycle. The lapatinib will be given as a single daily dose of 1250 mg orally.

3.2.2 Cycle 3 and beyond. The dose of temozolomide for cycle 3 and subsequent treatment cycles will depend upon the tolerance of the first 2 cycles. Patients who do not experience any grade 1 or greater myelotoxicity (white blood cell count, absolute neutrophil count or platelet count) will be eligible to have the temozolomide dose increased to 150 mg/m^2 as a single daily dose on days 1-7 and 15-21 of a 28-day cycle. The lapatinib dose will not be increased.

3.2.2.1 The dose will be determined using the body surface area (BSA) calculated at the beginning of each odd treatment cycle unless significant (> 3 kg) weight loss or gain is observed. The BSA will be calculated from the height obtained at the pretreatment visit and from the weight obtained at the visit before each odd cycle. Capsules of temozolomide are available in 5, 20, 100, 140, 180 and 250 mg. The daily dose will be rounded to the nearest 5 mg. The exact dose administered should be recorded in the CRF. Each daily dose should be given with the least number of capsules.

3.2.2.2 Prior to each treatment cycle with temozolomide a complete blood count (CBC) will be obtained (within 72 hours prior to dosing). The start of the first cycle will be scheduled within 7 days of registration. The start of all subsequent cycles (2-24) will be scheduled every 4 weeks (28 ± 3 days) after the first daily dose of temozolomide of the preceding cycle.

3.2.2.3 Patients will be instructed to fast at least 2 hours before and 1 hour after temozolomide administration, and 1 hour before or 1 hour after lapatinib administration. Water is allowed during the fast period. Patients will be instructed to swallow the capsules whole, in rapid succession, without chewing them. If vomiting occurs during the course of treatment, no re-dosing of the patient is allowed before the next scheduled dose.

3.2.2.4 Antiemetic prophylaxis with a 5-HT3 antagonist is strongly recommended and should be administered 30 to 60 minutes before temozolomide administration

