### 3.3.2 Temozolomide

**3.3.2.1** Dosing is based on adverse events (AEs) during the prior treatment cycle. If multiple AEs are seen, the dose administered should be based on the dose reduction required for the most severe grade of any single AE.

Dose Level	Dose mg/m^2	Remarks
- 2	75	Reduction if prior AE
-1	100	Reduction if prior AE
0	125	Starting dose for cycle 1 and 2, increase to 150 mg/m  for cycle 3 and beyond if non hematologic toxicity $\leq$ grade 2 and hematologic toxicity $\leq$ grade 1
+1	150	Highest possible dose level

**3.3.2.1.1** First and Second Cycle: Temozolomide will be started at a dose of 125mg/m^2/day.

**3.3.2.1.2** Third Cycle: The dose of temozolomide will be determined according to: (1) treatment related non-hematologic AE during the preceding treatment cycle, as well as (2) the worst ANC and platelet counts.

**3.3.2.1.3** Delay: On day 1 of each cycle (within the prior 72 hours), ANC  $\geq$  1.5 x 10^9/L, platelet count  $\geq$  100 x 10^9/L and all grade 2, 3 or 4 non-hematologic AEs (except for alopecia, nausea, and vomiting) must have resolved (to grade  $\leq$  1).

**3.3.2.1.4** If AEs persists, treatment should be delayed by 1 week for up to 4 consecutive weeks. If, after 4 weeks of delay, all treatment related AEs have still not resolved (to grade  $\leq$  1): then any further treatment with temozolomide should be stopped.

**3.3.2.1.5** Dose Escalations and Reductions: If, during the first and second cycle, all hematologic AEs observed were  $\leq$  grade 1 and treatment related non-hematologic AEs observed were grade  $\leq$  2 (except alopecia, lymphopenia, nausea and vomiting) then the temozolomide dose should be escalated to dose level 1 and this dose should be used as the starting dose for subsequent cycles. If treatment after cycles 1 and 2 temozolomide has to be delayed because of ongoing non-hematologic AEs of grade  $\geq$  2, then no escalation is possible. If the dose was not escalated at cycle 3, then the dose should not be escalated in further cycles (4-24).

**3.3.2.1.5.1** Dose reductions: If any treatment related non-hematologic AE observed was grade  $>$  2 (except alopecia, lymphopenia, nausea and vomiting) and/or if platelets  $<$  50 x 10^9/L and/or ANC  $<$  1 x 10^9/L, then the dose should be reduced by one dose level. Patients who require more than two dose reductions will have treatment stopped.

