**3.3.2.3 Worst Treatment-Related Hematologic AE During the Previous Cycle**

Worst AE		Platelets		
		<math>\geq 100 \times 10^9/L</math>	<math>50 - 99 \times 10^9/L</math>	<math>< 50 \times 10^9/L</math>
	<math>\geq 1.5 \times 10^9/L</math>	Dose unchanged	Dose unchanged	Reduce by 1 dose level
ANC	<math>\geq 1 & < 1.5 \times 10^9/L</math>	Dose unchanged	Dose unchanged	Reduce by 1 dose level
	<math>< 1 \times 10^9/L</math>	Reduce by 1 dose level	Reduce by 1 dose level	Reduce by 1 dose level

**Note:** A complete blood count must be performed on days 14 and 28 ( $\pm$  72 hours) after the first daily dose of each treatment cycle.

Hematologic AE on Day 1 of Each Cycle (within the prior 72 hours before Day 1)	
AE	Delay
ANC <math>< 1.5 \times 10^9/L</math> and/or Platelet count <math>< 100 \times 10^9/L</math>	Delay up to 4 weeks until all resolved. If unresolved after 4 weeks then stop. If resolved, dose delay/reductions based on non-hematologic AEs are applicable. If treatment has to be delayed for AEs, then no escalation is possible.

Non-Hematologic AE (except for alopecia, nausea, and vomiting) On Day 1 of Each Cycle (within the prior 72 hours)	
Grade	Delay

2-4	Delay up to 4 weeks until all resolved (to grade $\leq 1$ ). If unresolved after 4 weeks, then stop. If resolved, dose delay/reductions based on ANC and platelets are applicable. If treatment has to be delayed for AE, then no escalation is possible.
------------	---

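### For a patient with worst grade 1 WBC, ANC or platelet toxicity in cycles 1–2, the protocol points to two different temozolomide doses from cycle 3 (125 or 150 mg/m²) and does not say which rule governs

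*Combined protocol and SAP*

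**What the plan says.** Five places state when temozolomide may rise from 125 to 150 mg/m² at cycle 3.

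- **Précis (Design) and section 3.1:** "Patients who do not experience any grade 1 or greater myelotoxicity will be eligible to have the temozolomide dose increased".
- **Section 3.2.2 (cycle 3 and beyond):** the same condition with the counts named: "Patients who do not experience any grade 1 or greater myelotoxicity (white blood cell count, absolute neutrophil count or platelet count) will be eligible" for 150 mg/m².
- **Section 3.3.2.1, dose-level table, level 0:** the dose goes to 150 mg/m² "for cycle 3 and beyond if non hematologic toxicity" is at most grade 2 and hematologic toxicity is at most grade 1.
- **Section 3.3.2.1.5:** "If, during the first and second cycle, all hematologic AEs observed were" grade 1 or lower, and treatment-related non-hematologic AEs were grade 2 or lower (alopecia, lymphopenia, nausea and vomiting excepted), "then the temozolomide dose should be escalated to dose level 1 and this dose should be used as the starting dose for subsequent cycles".

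Two further provisions bear on the decision. The day 1 hematologic table in section 3.3.2.3 adds: "If treatment has to be delayed for AEs, then no escalation is possible". Section 3.3.2.1.5 makes a decision not to escalate final: "If the dose was not escalated at cycle 3, then the dose should not be escalated in further cycles (4-24").

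**The concern.** The first three places set the bar at grade 0 and the last two set it at grade 1 or lower. Both rules look at cycles 1–2 and both fix the cycle 3 dose. A patient whose worst count toxicity was grade 1 therefore stays at 125 mg/m² under one rule and goes to 150 mg/m² under the other.

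The trial is multi-center (sections 7.5 and 7.7), so sites can treat identical counts differently, and a patient held at 125 mg/m² cannot be escalated later. This bears on the adverse event and tolerability objective (1.1.2.2). The safety and laboratory summaries planned in section 8 would not show which rule had been used. There is also an audit question: section 7.2.8 counts any departure from the approved protocol as a deviation, and section 7.4.1 requires all deviations to be reported.

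**Working it through.** The plan gives no figure to reproduce here. The check compares the texts and then works out dose.

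**1. The two rules side by side.** Assume other hematologic AEs were grade 1 or lower, treatment-related non-hematologic AEs were grade 2 or lower (listed exceptions aside), and no cycle was delayed for AEs.

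| Worst WBC, ANC or platelet grade, cycles 1–2 | Précis, 3.1, 3.2.2 | 3.3.2.1 table, 3.3.2.1.5 |
|---|---|---|
| 0 | 150 permitted | 150 directed |
| 1 | 125, by implication | 150 directed |
| 2 or higher | 125 or lower | 125 or lower |

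Under these conditions the conflict is confined to the grade 1 row.

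**2. Does anything else settle that row?**

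- The delay rules in 3.3.2.1.5 and 3.3.2.3 block escalation only for patients whose treatment was delayed.
- The ANC-by-platelet grid in 3.3.2.3 says when a dose is unchanged or reduced. It sets no condition for escalation.
- The teleconference in section 7.8.1 discusses patients but states no criterion.
- Section 6.1.3 counts an abnormal laboratory value as an AE only if it causes signs or symptoms or needs therapy. If an asymptomatic grade 1 count is therefore not an AE, 3.3.2.1.5 still directs escalation, while 3.2.2 refers to the counts themselves. The conflict remains.

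**3. Dose per 28-day cycle.** Temozolomide is given on days 1–7 and 15–21, which is 14 dosing days (section 3.2.1).

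- At 125 mg/m²: 14 × 125 = 1750 mg/m²
- At 150 mg/m²: 14 × 150 = 2100 mg/m²
- Difference: 2100 − 1750 = 350 mg/m²; 350 / 1750 = 20%

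**4. Cumulative difference, no later reduction.**

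- Only cycle 3 given: 1 × 350 = 350 mg/m²
- Stop after cycle 12, an option under section 3.4.2 for patients with response or clinical benefit: cycles 3–12, 10 × 350 = 3500 mg/m²
- Maximum of 24 cycles: cycles 3–24, 22 × 350 = 7700 mg/m². Totals are 24 × 1750 = 42000 against 2 × 1750 + 22 × 2100 = 49700 mg/m², and 7700 / 42000 = 18.3%

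**5. Who can still benefit from a wording change?** Section 2.3 states that accrual is closed. Section 3.2.2.2 gives the timing: "The start of the first cycle will be scheduled within 7 days of registration", and later cycles follow at 28 ± 3 days. An undelayed cycle 3 starts at most 7 + 31 + 31 = 69 days after registration. A patient past that decision is not helped by new text.

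**The case against.** The best reply is that the two texts differ in force. The Précis, 3.1 and 3.2.2 say who is eligible and expressly forbid nothing. Section 3.3.2.1.5 is headed for escalations and reductions, is directive, and carries the non-hematologic and delay conditions that 3.2.2 lacks. On this view 3.2.2 is an incomplete summary, and escalating a grade 1 patient obeys an instruction and breaks only an implication.

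The difference in force stands: the two choices are not equally open to being called deviations. It does not remove the conflict. If grade 1 patients are to be escalated, the restriction written in three places does no work. Section 3.2.2 is itself specific, since it addresses cycle 3 and beyond and names its counts. No clause gives 3.3.2 precedence.

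Two other replies also stand. With accrual closed, the wording change may reach few patients or none. And the cautious rule is not free: section 1.2.5 supports the schedule with a week-on, week-off study at 150 mg/m²/day.

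A reader might go further than the documents allow in three ways.

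- **A count of affected patients.** The share with worst grade 1 counts is not given. Any assumed share would have to be cut again for the other toxicity conditions and the no-delay condition.
- **Harm to the primary endpoint.** Section 8 counts treatment-precluding toxicity as failure, so a link is conceivable. But both doses are protocol doses, 3.3.2 reduces the dose after toxicity, and the documents give nothing from which to size an effect.
- **An equally firm conflict in the other direction**, for example grade 2 anemia with clean WBC, ANC and platelets. Eligibility under 3.2.2 can be read as necessary but not sufficient, so both texts are satisfied by staying at 125 mg/m².

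**Conclusion.** The point holds for one defined patient: worst WBC, ANC or platelet toxicity of grade 1 in cycles 1–2, other hematologic AEs grade 1 or lower, treatment-related non-hematologic AEs grade 2 or lower with the listed exceptions, and no AE delay. For that patient the plan supports 125 mg/m² by implication and 150 mg/m² by direction. This is a contradiction in an operative dosing rule.

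The 20% difference per cycle is exact. The cumulative range of 350 to 7700 mg/m² depends on the number of cycles given and assumes no later reduction; the documents attach no safety threshold to cumulative dose. The number affected is not derivable. The sample size and stopping rule do not depend on which rule applies. What is at stake is consistent dosing and a tolerability report that can be interpreted. It should be fixed.

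**What to change.** State one criterion identically in the Précis, 3.1, 3.2.2, the 3.3.2.1 table and 3.3.2.1.5, graded on CBC values with each count named. Unless the sponsor documents that the 3.3.2 rule was intended, use the cautious one. Escalate at cycle 3 only if, in cycles 1–2:

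- WBC, ANC and platelets were all grade 0;
- hemoglobin toxicity was grade 1 or lower;
- lymphopenia is excepted, as 3.3.2.1.5 now does, but listed with the hematologic conditions so that its status is clear;
- treatment-related non-hematologic AEs were grade 2 or lower, with the existing exceptions;
- there was no delay for AEs.

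For patients already past the cycle 3 decision, report which rule was applied and how many were escalated, by worst cycle 1–2 hematologic grade (0, 1, 2 or higher). The table should be descriptive, because escalated patients were selected for tolerating cycles 1–2.

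The cost is wording edits in five places, with IRB approval of the amendment and a site memo if any patient still faces the decision. The table needs no new assessments: exact dose is recorded in the CRF (3.2.2.1) and CBC is taken every two weeks (3.7.5). The downside of the cautious rule is that fewer patients reach 150 mg/m².

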### **3.3 DOSE MODIFICATION**

#### **3.3.1 Lapatinib**

**3.3.1.1 First Cycle:** Lapatinib will be started at 1250 mg once a day as continuous oral dosing. There is no dose escalation from the starting dose.

Dose Level	Dose Schedule once a day	Remarks
- 2	750 mg	Reduction if prior AE
-1	1000 mg	Reduction if prior AE
0	1250 mg	Starting dose

### 3.3.1.2 Summary of dose modifications

Dermatologic		
Rash – acne/acneiform 

• Intolerable Grade 2 & Grades 3-4

		
Hold dose.
 

• Re-evaluate at least weekly until AE resolved to <math>\leq</math> 1 or tolerable Grade 2.

• Re-treat at a one dose level reduction

• If AE persists <math>></math> 4 weeks, remove patient from study

 
Patients with Grade 4 AEs related to agent should be taken off study.
 
Note: Grade 2 lapatinib related rash may not automatically require dose reduction. However, for Grade <math>\geq</math> 3 rash or recurrent intolerable Grade 2 rash, reduce 1 dose level.

Gastrointestinal		
Diarrhea 

• Grade 1

• Grade 2

• Grade 3, 4 or intolerable Grade 2:

		
No intervention required
 
Loperamide (4 mg at first onset, followed by 2 mg every 2–4 hrs until diarrhea free for 12 hrs)
 

• Hold dose.

• Loperamide, hold agent until recovery to <math>\leq</math> Grade 1 and then reduce 1 dose level

• If AE persists <math>></math> 4 weeks, remove patient from study

• Patients with Grade 4 AEs related to agent may be taken off study at investigator's discretion.

Ocular/Visual		
Keratitis 

• Grade 1

		

• Preservative-free artificial tears, ointments, and/or other therapies as clinically indicated, with a follow-up examination within 2 weeks.

• Dose reduction not required.

• Grade 2 or 3

		

• Manage as for Grade 1 keratitis.

• Grade 2 persistent (>14 days) or Grade 3: Hold dose. Re-treat at a reduced dose after resolution or amelioration of AE to <math>\leq</math> Grade 1 at the discretion of the investigator.

• Persistent Grades 2 or 3: Remove patient from study for persistent Grade <math>\geq 2</math> keratitis after dose held for 14 days. Ophthalmologic F/U should be scheduled at a frequency determined by the ophthalmologist

Pulmonary/Upper Respiratory		
Signs and symptoms of Interstitial Pneumonitis		
Patient should be thoroughly evaluated, closely monitored, and supported as clinically indicated.
 
Hold dose pending diagnosis
 
Permanently discontinue lapatinib if diagnosis is confirmed and considered possibly related to lapatinib.

All other non-hematologic adverse events		
Any Grade 2 of concern (e.g., prolonged cardiac,		
Hold dose.
 

• Re-treat at a reduced dose after resolution or amelioration of AE to <math>\leq</math> Grade 1

 
If AE persists <math>> 4</math> weeks , remove patient from study

Grade 3 or 4		
Hold dose.
 

• Re-evaluate until AE resolved to <math>\leq</math> Grade 1 (or tolerable Grade 2).

• If AE persists <math>> 4</math> weeks, remove patient from study

• Patients with Grade 4 AEs related to agent may be taken off study at investigator's discretion.

### 3.3.1.3 Liver Chemistry Stopping and Follow-up Criteria

#### 3.3.1.3.1 Liver Chemistry Stopping Criteria

3.3.1.3.1.1 Liver chemistry stopping and follow up criteria have been designed to assure subject safety and evaluate liver event etiology. All subjects who meet liver chemistry criteria requiring permanent discontinuation of lapatinib must continue to be followed for the study assessments and procedures as defined in Section 3.7.6 and Appendix 12.5. If a subject experiences  $ALT > 3 \times ULN$  and total bilirubin  $> 2.0 \times ULN$  ( $> 35\%$  direct; bilirubin fractionation required\*), then the following actions must be taken:

- immediately and permanently discontinue investigational product;
- complete the SAE data collection tool, and the clinical evaluation CRF;
- in addition to the liver event follow up assessments defined below, the following are suggested: specialist or hepatology consultation; anti-nuclear antibody, anti-smooth muscle antibody, and Type 1 anti-liver kidney microsomal antibodies; and liver imaging and/or liver biopsy to evaluate liver disease;
- promptly report the event to NCI CCR within 24 hours of learning of its occurrence (refer to Section 7.4);
- monitor every week until liver chemistries resolve, stabilize or return to within baseline values;
- do not re-challenge with lapatinib.
- **NOTE:** bilirubin fractionation should be performed if testing is available. If testing is unavailable and a subject meets the criterion of total bilirubin  $> 2.0 \times ULN$ , then the aforementioned actions must still be performed.

#### 3.3.1.3.1.2 If a subject experiences:

- $ALT > 8 \times ULN$  or
- $ALT > 5 \times ULN$  persisting for  $\ge 2$  weeks: retest within 3 days from the first occurrence and then weekly to determine if ALT elevation persists or
- $ALT > 3 \times ULN$  with signs or symptoms of hepatitis or hypersensitivity (the appearance or worsening of fatigue, nausea, vomiting, right upper quadrant pain or tenderness, fever, rash, or eosinophilia),
- Total Bilirubin  $> 2 \times ULN$  in absence of Gilbert's Syndrome

then hold investigational product for 2 weeks, repeat liver chemistry testing in 2 weeks, and then call the Study Chair ([name]) to discuss the possibility of re-challenging with investigational product.

